6.9.1.2. Secondary Analysis of the Primary Efficacy Outcome

This secondary analysis is to evaluate the non-inferiority of LY3298176 to dulaglutide for the change in HbA1c from baseline to 26 weeks, using the primary analysis model. This secondary objective will be met if the upper limit for the 90% credible interval for the difference between LY3298176 and dulaglutide less than 0.3% (non-inferiority margin) for at least one LY3298176 dose arm.

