3.2. Background

3.3. Benefit/Risk Assessment

More information about the known and expected benefits, risks, serious adverse events (SAEs), and reasonably anticipated AEs of LY3298176 may be found in the Investigator's Brochure (IB). Information on AEs expected to be related to the investigational product may be found in Section 7 (Development Core Safety Information) of the IB. Information on SAEs that are expected in the study population independent of drug exposure will be assessed by the sponsor in aggregate, periodically during the course of the study, and may be found in Section 6 (Effects in Humans) of the IB.

More detailed information about the known and expected benefits and risks of dulaglutide may be found in the USPI or SmPC (Trulicity® USPI, 2015; Trulicity® SmPC, 2016).

4. Objectives and Endpoints

Table GPGB.1shows the objectives and endpoints of the study.

Table GPGB.1. Objectives and Endpoints

Objectives	Endpoints
Primary The primary objective of this study is to demonstrate a dose–response relationship of QW SC injections of LY3298176 on HbA1c change from baseline relative to placebo, in patients with T2DM inadequately controlled with diet and exercise alone or treated with a stable dose of metformin.	The change in HbA1c from baseline to 26 weeks
 Secondary To determine the effect of LY3298176 versus dulaglutide (and to compare the effect of each versus placebo) on: The mean body weight change from baseline to 12 and 26 weeks The percentage of patients with 5% or greater body weight loss at 26 weeks The change from baseline of HbA1c at 12 weeks The percentage of patients with 10% or greater body weight loss at 26 weeks The percentage of patients reaching the HbA1c target of ≤6.5% and of ≤7.0%. The change from baseline of fasting blood glucose (FBG) at 12 and 26 weeks The change from baseline to 26 weeks in high-density lipoprotein cholesterol (HDL-C), total cholesterol, triglycerides, and low-density lipoprotein cholesterol (LDL-C) 	 The change in mean body weight from baseline to 12 and 26 weeks The percentage of patients with 5% or greater body weight loss from baseline to 26 weeks The change in HbA1c from baseline to 12 weeks The percentage of patients with10% or greater body weight loss from baseline to 26 weeks The percentage of patients reaching the HbA1c target of ≤6.5% and of ≤7.0% The change in FBG from baseline to 12 and 26 weeks The change in lipid laboratory data from baseline to 26 weeks

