5.3. Determination of Sample Size

Approximately 300 patients will be randomized to placebo, dulaglutide, or 1 of the 4 LY3298176 treatment arms assuming a 10% dropout rate resulting in approximately 45 completers per arm.

The Bayesian approach using a dose-response model with respect to an HbA1c change from baseline to 26 weeks will provide approximately 98% probability to show with 90% confidence that at least 1 LY3298176 dose has superior glycemic control over placebo with a superiority bound of -0.8%. The sample size also provides >95% probability to show with 80% confidence that at least 1 LY3298176 dose has non-inferior glycemic control compared with dulaglutide from baseline to 26 weeks with a 0.3% non-inferiority bound. This assumes a profile for the change in HbA1c from baseline to 26 weeks shown in Table 5.1, and a standard deviation (SD) of 1.0%.

In addition, this sample size also provides approximately 89% probability to show with 60% confidence that at least 1 LY3298176 dose has superior weight loss compared with dulaglutide from baseline to 26 weeks with a superiority bound of -2 kg. This assumes a profile for the change in body weight from baseline to 26 weeks shown in Table 5.1, and an SD of 6 kg.

Table 5.1. Dose-Response Assumption Used in Sample Size Determination

	Placebo	LY 1	LY 5	LY 10	LY 15	Dulaglutide
CFBL HbA1c (%)	0%	-0.74%	-1.17%	-1.29%	-1.44%	-1.28%
CFBL Body Weight (kg)	0	-2.0	-3.0	-5.0	-6.0	-2.5

Abbreviations: CFBL = change from baseline; HbA1c = hemoglobin A1c; LY = study drug LY3298176.

6. A Priori Statistical Methods

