6.1. General Considerations

Statistical analysis of this study will be the responsibility of Lilly or its designee. Any change to the statistical methods described in the protocol will require an amendment only if it changes a principal feature of the protocol. Any other change to the statistical analyses and the justification for the change will be documented in the clinical study report. Additional exploratory analyses of data may be conducted as deemed appropriate without further changes made to the protocol or SAP even after the database lock (DBL).

Tests of treatment effects will be conducted at a one-sided alpha level of 0.1 and/or one-sided 90% credible interval (CI) for the Bayesian dose response analysis, and at a two-sided alpha level of 0.05 for other analyses, unless otherwise stated. No adjustments for multiplicity will be performed.

The baseline visit will be Visit 3. The baseline values used for the analyses will be the last scheduled baseline value obtained for each patient prior to first dosing. For all variables, if baseline data are not available or if they are missing, then the last non-missing measurement taken prior to first treatment will be used for the baseline measurement.

All efficacy and safety data will be summarized by each treatment group at each scheduled visit unless otherwise indicated. A scheduled visit is based on the actual visit number reported by the site. Imputed data may be applied in model-based data analysis, but will not be used in data listing.

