6.9.1.3. Supporting Analyses of Primary Outcome

The following supportive analyses will be performed for the primary outcome:

- An analysis using the same statistical model as the primary analysis will also be performed using mITT population on treatment without rescue dataset.
- The change in HbA1c from baseline will be analyzed using MMRM with restricted maximum likelihood estimation described in section 6.1.1. Comparisons between each LY3298176 dose arm with dulaglutide and placebo will be made. This analysis will be performed on three analyses sets: mITT population on treatment without rescue data, mITT population with all data, and PP dataset.
- An ANCOVA model will be used on the last observation carried forward (LOCF) endpoint of HbA1c as described in section 6.1.2. using MITT on treatment without rescue, and mITT population.

Table 6.3 describes the analyses to meet the primary objective, all performed on the HbA1c change from baseline values, including the above sensitivity analyses.

Analysis Type	LOCF or Observed Values	Analysis Set
Hierarchical Logistica	Observed	mITT without
		rescue
Hierarchical Logistic	Observed	mITT on treatment
		without rescue
MMRM	Observed	mITT
MMRM	Observed	PP
MMRM	Observed	mITT on treatment
		without rescue
MMRM, subgroup analyses	Observed	mITT on treatment
		without rescue
ANCOVA	LOCF	mITT on treatment
		without rescue,
		mITT

Table 6.3. Summary of Analyses for Primary Outcome

Abbreviations: ANCOVA = analysis of covariance; HbA1c = hemoglobin A1c; LOCF = last observation carried forward; mITT = modified intent-to-treat; MMRM = mixed model repeated measures; PP = per protocol.

a primary analysis

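### The non-inferiority rule against dulaglutide never asks whether dulaglutide beat placebo in this trial, so on its own it barely separates a successful trial from one in which nothing works

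*SAP*

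**What the plan says.** **The rule.** SAP 6.9.1.2 uses the primary Bayesian model. The objective is met if the upper limit of the 90% credible interval shows a "difference between LY3298176 and dulaglutide less than 0.3% (non-inferiority margin) for at least one LY3298176 dose arm". That is the whole condition. SAP 6.9.2.1 carries the 0.3% margin over to 12-week HbA1c and adds no further condition. SAP 6.1 sets the general level as a "one-sided alpha level of 0.1 and/or one-sided 90% credible interval (CI) for the Bayesian dose response analysis", and states "No adjustments for multiplicity will be performed".

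**Contrasts with placebo.** In SAP 6.9.1.1 the Bayesian contrasts with placebo run over d = 1 to D-1. Dulaglutide is d = D, so it is left out. For the supportive MMRM, SAP 6.9.1.3 says "Comparisons between each LY3298176 dose arm with dulaglutide and placebo will be made". Neither place names dulaglutide against placebo.

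**The protocol.** Table GPGB.1 (Protocol section 4) sets out to determine the effect of LY3298176 against dulaglutide "and to compare the effect of each versus placebo" on a list of secondary endpoints. The list includes 12-week HbA1c but not 26-week HbA1c change, which is the primary endpoint. SAP 4.2 restates the objective as LY3298176 against dulaglutide and placebo, and the comparison of dulaglutide with placebo is gone. Protocol 10.3.3.3.1 sets up the 26-week non-inferiority analysis, also without such a condition, and reserves it for internal business decisions.

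**The concern.** A non-inferiority conclusion is informative only if the comparator worked in the trial at hand. If dulaglutide underperforms, an LY3298176 dose with little effect can fall within 0.3% of it, and the rule cannot tell parity with a working drug from parity with an inactive one. A three-way design can check this directly, but the rule does not use the placebo arm.

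Dilution is not far-fetched. The rationale for the protocol amendment records missed doses and study drug lost through lack of refrigeration after hurricanes. SAP 6.9 also keeps data after treatment discontinuation in the primary analysis set, removing only data after rescue. Both shrink differences between arms, which favours non-inferiority. Protocol 5.4 makes the trial the main basis for Phase 3 dose selection, so an internal reading of the result still matters.

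**Working it through.** **Inputs.** SAP 5.3 gives "a standard deviation (SD) of 1.0"%, "assuming a 10% dropout rate resulting in approximately 45 completers per arm", and the margin "with a 0.3% non-inferiority bound". Table 5.1 gives HbA1c changes of 0 for placebo, -0.74, -1.17, -1.29 and -1.44 for the four doses, and -1.28 for dulaglutide. The one-sided 90% reading (SAP 6.1) gives z = 1.2816.

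**Formula.** Let s = 1.0/√45 = 0.1491 and SE = s√2 = 0.2108. With independent arm means and one shared comparator,

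P(at least one dose passes) = 1 − ∫ φ(u) ∏ [1 − Φ((m − z·SE + s·u − δ_d)/s)] du,

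where m is the margin and δ_d is the true difference of dose d from the comparator.

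**The plan's own figures.**
- Superiority to placebo, bound −0.8%, 90% confidence: 98.3% (stated: about 98%).
- Non-inferiority at 80% confidence, δ = 0.54, 0.11, −0.01, −0.16: 95.04% (stated: more than 95%).
- Non-inferiority at the 90% level of the decision rule: 87.7%.

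**No arm works (all δ = 0).** A dose passes if its observed difference is below 0.3 − 1.2816 × 0.2108 = 0.0298. The probability is Φ(0.0298/0.2108) = Φ(0.141) = 55.6% per dose, and 84.3% for at least one of four. Fitting the SAP's hierarchical logistic model and priors to 1,500 simulated complete-data trials, without ITP imputation, gives 84.5% with placebo in the fit and 85.5% without it.

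| Variation | Pass rate, no arm works |
|---|---|
| Base case | 84.3% |
| n = 50 per arm | 86.4% |
| SD 0.9 / 1.2 | 88.4% / 76.7% |
| Two-sided 90% interval | 72.0% |
| 80% confidence | 93.7% |

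**Diluted effects** (1,000,000 simulated trials):

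| All effects at | Non-inferiority met | Primary objective met |
|---|---|---|
| one half of plan | 83% | 7% |
| one quarter of plan | 82% | 0.07% |

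At one half, non-inferiority is met while the primary fails in 76% of trials.

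**Adding the condition that dulaglutide beats placebo** (one-sided 90%):
- No arm works: the pass rate falls from 84.4% (simulated) to 4.9%.
- Planned effects: the condition holds with probability Φ(1.28/0.2108 − 1.2816) = Φ(4.79), above 99.99%. Power is 87.6% in the simulation with or without it.
- Effects halved: the condition holds with probability Φ(0.64/0.2108 − 1.2816) = Φ(1.75), or 96%. The loss is about 4 points.
- LY3298176 as planned, dulaglutide without effect: the condition holds only 10% of the time by construction, so the label is withheld in about 90% of trials.

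**The case against.** **The primary analysis already guards against the worst case.** It compares every dose with placebo against a −0.8% bound and also reports posterior probabilities at other thresholds. If no arm works, the primary objective is met about once in a million trials. A reader might infer that a trial in which nothing works could pass unnoticed, and the documents do not support that. What remains is that non-inferiority is not formally conditional on the primary result, and that LY3298176 against placebo does not show that dulaglutide performed.

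**The 84% is not an error rate.** A reader might take it for a false-positive rate. With equal arms LY3298176 truly is non-inferior, so the statement is correct but uninformative. At the real boundary, with all doses 0.3% worse than dulaglutide, the rule passes 25.9% of the time. That figure reflects unadjusted any-of-four testing, a separate matter that the SAP states openly.

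**The protocol mismatch is narrower than it may look.** A reader might infer that SAP 6.9.1.2 departs from the protocol. It does not: the protocol phrase covers the listed secondary endpoints, and Protocol 10.3.3.3.1 has no such condition for 26-week HbA1c. The mismatch lies in SAP 4.2 and reaches a non-inferiority margin only at 12 weeks.

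**The contrast is estimable.** SAP 6.9 puts all treatment groups in every model except the dose-response analyses, and SAP 6.1.1 allows between-treatment intervals. It is unnamed, but not out of reach.

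**Conditioning on the primary objective is an alternative.** It leaves about 0.0001% passing when no arm works and 86.6% power under plan. But if effects are halved it leaves only 83% − 76% = 7%, because the −0.8% bound is demanding, and it still says nothing about dulaglutide.

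**Conclusion.** The point stands as a gap in what the rule can conclude. By itself the rule passes about 84% of the time when no arm works and about 88% under the planned effects. The figures assume 45 completers per arm, an SD of 1.0%, independent arm means and a one-sided 90% limit. SAP 6.1 supports the one-sided reading, but 6.9.1.2 does not say which it means; a two-sided interval gives 72% under no effect. The consequence is limited by the primary comparison with placebo and by the protocol's restriction to internal decisions, although SAP 6.9.1.2 does not repeat that restriction. The change is worth making because it costs almost nothing under the planning assumptions.

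**What to change.** - **SAP 6.9.1.2 and 6.9.2.1:** add the dulaglutide-minus-placebo contrast at 26 and 12 weeks. State non-inferiority as a conclusion only when the one-sided 90% limit of that contrast favours dulaglutide. Otherwise report the LY3298176-minus-dulaglutide estimate and interval without that conclusion.
- **Source of the contrast:** take it from the planned all-arm MMRM and name the analysis set, because the primary set (mITT without rescue) is not among the three MMRM sets in 6.9.1.3. The Bayesian run could supply it instead once the sponsor confirms which FACTS file applies. The footnote to Table 6.2 says separate files serve the placebo and dulaglutide comparisons, with x_0 = 1 in the latter.
- **SAP 4.2 and 6.9.1.3:** restore dulaglutide against placebo.
- **SAP 6.9.1.2:** say that the 90% limit is one-sided, if that is meant.

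The cost is SAP wording and one contrast from a model already planned. There is no power loss under plan and about 4 points if all effects are halved. Where LY3298176 works and dulaglutide does not, the non-inferiority label is lost in about 90% of trials, but superiority of LY3298176 to placebo and to dulaglutide can be reported instead.

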6.9.1.3. Supporting Analyses of Primary Outcome

The following supportive analyses will be performed for the primary outcome:

- An analysis using the same statistical model as the primary analysis will also be performed using mITT population on treatment without rescue dataset.
- The change in HbA1c from baseline will be analyzed using MMRM with restricted maximum likelihood estimation described in section 6.1.1. Comparisons between each LY3298176 dose arm with dulaglutide and placebo will be made. This analysis will be performed on three analyses sets: mITT population on treatment without rescue data, mITT population with all data, and PP dataset.
- An ANCOVA model will be used on the last observation carried forward (LOCF) endpoint of HbA1c as described in section 6.1.2. using MITT on treatment without rescue, and mITT population.

Table 6.3 describes the analyses to meet the primary objective, all performed on the HbA1c change from baseline values, including the above sensitivity analyses.

Analysis Type	LOCF or Observed Values	Analysis Set
Hierarchical Logistica	Observed	mITT without
		rescue
Hierarchical Logistic	Observed	mITT on treatment
		without rescue
MMRM	Observed	mITT
MMRM	Observed	PP
MMRM	Observed	mITT on treatment
		without rescue
MMRM, subgroup analyses	Observed	mITT on treatment
		without rescue
ANCOVA	LOCF	mITT on treatment
		without rescue,
		mITT

Table 6.3. Summary of Analyses for Primary Outcome

Abbreviations: ANCOVA = analysis of covariance; HbA1c = hemoglobin A1c; LOCF = last observation carried forward; mITT = modified intent-to-treat; MMRM = mixed model repeated measures; PP = per protocol.

a primary analysis

6.9.2. Efficacy - Secondary Outcomes

6.9.2.1. Dose Response Analyses on HbA1c and Body Weight

Change from baseline in HbA1c at 12 weeks will be accessed using a superiority margin of - 0.8% to placebo as well as a non-inferiority margin of 0.3% to dulaglutide, based on the primary analysis model.

The body weight change from baseline at both 12 and 26 weeks will compare to a superiority margin of -2 kg to placebo. Similar Bayesian dose-response analysis as for HbA1c will also be performed for the change in body weight, except with an exponential dose-response model:

$$\begin{aligned} \theta_{dT}{\sim}a + b*d^{\gamma} + \varsigma_{dT}, & d = 0, ..., D-1 \\ y_{T}{\sim}N(\theta_{dT}, \sigma^{2}), & \end{aligned}$$

 γ is a sigmoidicity parameter indicating shape or steepness of dose response. The priors for each parameters are: $\alpha \sim N(0, 50)$, $b \sim N(1, 10)$, $\gamma \sim N(1, 5)$. Other dose-response models may be explored if the exponential dose-response model does not fit the data well. The analysis will be performed in two datasets: mITT without rescue, and mITT on treatment without rescue.

6.9.2.2. Continuous Variable Analyses

The MMRM model described in Section 6.1.1 will be performed on the following variables to obtain inference for the corresponding secondary objectives:

- Body weight change from baseline
- Change from baseline of HbA1c

- Change from baseline of FBG
- Change from baseline of waist circumference

BMI (kg/m²) will be calculated at each visit at which weight is measured, using height as measured during screening. Change from baseline in BMI will be listed and summarized.

6.9.2.3. Analyses Based on Multiple Imputations

The MMRM model produces consistent estimator for missing at random (MAR). To understand the key efficacy results with potential missing not at random (MNAR), analyses will be further explored using selected pattern mixture models for missing data in the mITT population for the change in HbA1c and change in body weight. In this case, the missing data will be imputed using the non-missing data in the placebo arm through a multiple imputation procedure. The imputed 26-week HbA1c or body weight response for the missing data along with the non-missing 26-week data will be employed using an ANCOVA model or MMRM model. The parameter estimates and inferences will be calculated by method of Little and Rubin (1987).

6.9.2.4. Analyses on Variables with Percent of Patients Reaching a Target

The proportion of patients who have $\geq 5\%$ and $\geq 10\%$ body weight loss will be analyzed using a longitudinal logistic regression model with treatment, strata (baseline HbA1c category, and baseline BMI category) and metformin use (yes, no), visit, and treatment-by-visit interaction as fixed effects, and baseline body weight as a covariate.

The proportion of patients who have achieved an HbA1c level of <=7% and <=6.5% at 26 weeks will be analyzed by a logistic regression with factors treatment, baseline BMI category, and metformin use (yes, no) will be fixed effects and continuous baseline HbA1c level will be a covariate. Other HbA1C categories may be added.

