7.8. Treatment after the End of the Study

7.8.1. Special Treatment Considerations (Rescue Therapy)

Investigators will be trained on how to apply decision criteria for the timing and method of intervention in patients who do not reach glycemic targets during the 26-week treatment period. An additional therapeutic intervention should be considered in patients who meet the following criteria:

• The patients are fully compliant with assigned therapeutic regimen.

AND

- In the absence of any acute condition that raises blood glucose either of the following occurs:
 - Ouring the first 6 weeks post-randomization: An average fasting glucose level above 270 mg/dL (15.0 mmol/L) occurs over at least a 2-week period (at least 4 values/week must be available).

OR

O Any time after the first 6 weeks to 26 weeks post-randomization: An average fasting glucose level above 240 mg/dL (13.3 mmol/L) occurs over at least a 2-week period (at least 4 values/week must be available).

If these conditions are met, then patients may begin treatment with another antihyperglycemic agent as determined by their physician. If treatment with another antihyperglycemic agent is instituted, then study drug should be permanently discontinued. Patients may remain in the study for safety follow-up, but the date at which they begin rescue therapy will be the last date for collection of efficacy measures.

8. Discontinuation Criteria

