10.3. Statistical Analyses

10.3.1. General Statistical Considerations

Statistical analysis of this study will be the responsibility of Lilly or its designee. Any change to the statistical methods described in the protocol will require an amendment only if it changes a principal feature of the protocol. Any other change to the statistical analyses and the justification for the change will be described in the statistical analysis plan (SAP) and/or clinical study report. Additional exploratory analyses of the data may be performed as deemed appropriate. Analyses will be fully detailed in the SAP.

The intention-to-treat (ITT) population is defined as all randomized patients. Statistical analyses (including the primary analysis) will be conducted on the modified ITT (mITT) population. The mITT population is defined as all randomized patients with at least 1 post-baseline measurement according to the treatment the patients were assigned. The per-protocol (PP) population is defined as all randomized patients who were compliant with study drug and completed the protocol and is a subset of the mITT population. The safety population is defined as all randomized patients who have received at least 1 dose of study drug. Safety analyses will be performed on the safety population.

Some efficacy measures will also be analyzed on the PP dataset. The PP analysis will include patients who meet the following additional criteria:

- Have been appropriately randomized
- Have not discontinued from the study for any of the early discontinuation criteria
- Have not missed 4 or more doses during the treatment period
- Have not been rescued or taken a concomitant antihyperglycemic medication besides metformin for more than 7 cumulative days during the treatment period

Patients who have had rescue therapy will be included in the mITT population, but not the PP population. The efficacy measures will be censored at the time of rescue for analyses using mITT population.

No adjustments for multiplicity will be performed.

All tests of treatment effects will be conducted at a one-sided alpha level of 0.1 and/or one-sided 90% confidence interval, unless otherwise stated.

The baseline value used for the analyses will be the last scheduled baseline value obtained for each patient prior to randomization.

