6.9. Efficacy Analyses

The primary efficacy analysis, which is the Bayesian dose-response analysis on the change in HbA1c, will be performed on mITT population without rescue (i.e., data after use of rescue medication will not be included). Unless specified, all other efficacy analyses will be performed on mITT population on treatment without rescue (i.e., data after rescue medication or data after study treatment discontinuation will not be included). Some key efficacy measures, such as HbA1C and body weight, will also be analyzed on mITT population with all available data and on a PP dataset.

With the exception of the dose-response analyses on the HbA1c and body weight endpoints, all statistical models will include all treatment groups, including LY3298176, placebo, and dulaglutide.

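### The HbA1c target analysis uses only patients with an eligible week-26 value, so response rates and arm contrasts can be biased

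*SAP*

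**What the plan says.** SAP 6.9.2.4 treats two kinds of target differently.

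- **HbA1c at or below 7.0% and 6.5%:** the proportions "at 26 weeks will be analyzed by a logistic regression with factors treatment, baseline BMI category, and metformin use", plus continuous baseline HbA1c. There is no visit term.
- **Weight loss of at least 5% and 10%:** the proportions "will be analyzed using a longitudinal logistic regression model with treatment", strata, visit and treatment-by-visit interaction, plus baseline weight.

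The section names no analysis set, so the SAP 6.9 default applies: "Unless specified, all other efficacy analyses will be performed on mITT population on treatment without rescue". In that set "data after rescue medication or data after study treatment discontinuation will not be included". SAP 6.9 adds that "Some key efficacy measures, such as HbA1C and body weight, will also be analyzed on mITT population with all available data" and on a per-protocol dataset, without saying whether target attainment is among those measures.

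The protocol points the same way on rescue. Section 7.8.1 says that "the date at which they begin rescue therapy will be the last date for collection of efficacy measures", and section 10.3.1 says that "The efficacy measures will be censored at the time of rescue for analyses using mITT population".

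**The concern.** A single-visit logistic regression can use only patients who have an outcome at that visit. A patient rescued or taken off drug before week 26 has no eligible outcome under the default set, so the patient leaves both numerator and denominator.

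Such an analysis is sound if, given the covariates in the model, being excluded is unrelated to the week-26 response. The covariates are treatment, BMI category, metformin use and baseline HbA1c. Rescue is defined in Protocol 7.8.1 by average fasting glucose after randomisation, which none of these covariates captures and which is closely tied to later HbA1c. The condition is therefore doubtful even for the SAP's own on-treatment, without-rescue question.

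Target attainment is a secondary objective against both dulaglutide and placebo, in a trial meant to inform Phase 3 dose selection. Losses could differ between arms: the protocol provides for dose reduction for intolerance at 10 and 15 mg, and rescue may be commoner on placebo. Unequal loss can create or hide differences between doses.

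**Working it through.** **1. Does any rule bring the excluded patients back?**

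- Multiple imputation (SAP 6.9.2.3) covers change in HbA1c and change in body weight only.
- LOCF for HbA1c (SAP 6.9.1.3) belongs to the ANCOVA of continuous change.
- SAP 6.1 permits imputed data in model-based analyses but names no method for this endpoint.
- An HbA1c is taken at early termination, but SAP 6.1 assigns visits by the reported visit number and version 3 deleted the visit window, so nothing maps that value to week 26.

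None restores them. Yet HbA1c is scheduled at weeks 1, 2, 4, 8, 12, 16, 20 and 24, so most excluded patients will have usable earlier values.

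**2. The plan's own figure.** SAP 5.3 randomises about 300 patients equally to 6 arms with 10% dropout: 300/6 = 50 per arm, and 50 × 0.90 = 45 completers. This reproduces. No response rate or power is stated for the target endpoint.

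**3. Effect on one arm.** Let d be the fraction excluded, r the rate among those analysed, q the rate among those excluded, and R the rate in all patients:

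R = (1 − d)·r + d·q, so r = (R − d·q)/(1 − d).

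Only d = 10% is from the documents; R = 50% is assumed.

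- q = 0: r = 0.50/0.90 = 55.6%, an overstatement by a factor of 1.11.
- q = 50%: r = (0.50 − 0.05)/0.90 = 50.0%, no overstatement.

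Turned round, an observed r = 50% with d = 10% means R = 45%, 47.5%, 50% or 52.5% for q = 0, 25%, 50% or 75%. The overstatement can vanish or reverse.

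**4. Effect on contrasts.** Assume true rates of 15% (placebo) and 50% (active): difference 35 points, odds ratio (0.50/0.50)/(0.15/0.85) = 5.67. With q = 0 throughout, each analysed rate is R/(1 − d). The 20% losses are assumptions.

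| Loss, placebo / active | Placebo | Active | Difference | Odds ratio |
|---|---|---|---|---|
| 10% / 10% | 16.7% | 55.6% | 38.9 points | 6.25 |
| 20% / 10% | 18.8% | 55.6% | 36.8 points | 5.42 |
| 10% / 20% | 16.7% | 62.5% | 45.8 points | 8.33 |

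Two active arms both truly at 50%, with 20% and 10% loss, show 0.50/0.80 = 62.5% and 0.50/0.90 = 55.6%. That is a false gap of 6.9 points (odds ratio 1.33) in favour of the arm that lost more patients.

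**The case against.** **The exclusion is open and deliberate.** A reader might infer that patients are dropped silently. They are not: SAP 6.9 states the exclusion, the version 3 revision history explains it as better reflecting treatment effect, and the protocol censors at rescue. What is unstated is the resulting denominator.

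**The SAP leaves room for another handling.** It permits imputation in general and promises all-data analyses of some key measures. So the restriction to patients with an eligible value follows from the absence of any rule, not from an explicit one. But permission without a method is not a rule, and an all-data set need not recover rescued patients, because Protocol 7.8.1 ends their efficacy collection at rescue (Protocol 10.3.6.3 allows only exploratory analyses with rescued patients' data).

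**Rates too high in every arm?** A reader might infer this; the documents do not support it. They give no rescue rate and no target response rate. Rescued patients are plausibly non-responders, but patients stopping for intolerance may have been at target. Heavier placebo loss can lower the odds ratio, as in the second row of the table.

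**Non-responder counting asks a different question.** It makes rescue or discontinuation part of the outcome, whereas the SAP chose an on-treatment, without-rescue question. This stands: the gap between the two analyses is not by itself the bias.

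**The weight contrast and materiality.** Protocol 10.3.3.3.2 prescribes logistic regression for both kinds of target, so it is the weight analysis that the SAP changed. Week-26 HbA1c as a continuous outcome is well covered by the Bayesian model, MMRM, LOCF ANCOVA and multiple imputation. This limits the consequences but does not repair the target analysis.

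**Conclusion.** The point stands in conditional form. As written, the HbA1c target analysis uses only patients with an eligible on-treatment week-26 value. It discards earlier HbA1c data on the rest, and one reason for their absence, rescue, depends on post-baseline glucose. This is more than a missing detail, because the analysis can be biased even for the question the SAP chose.

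At the planned 10% dropout, the overstatement of an assumed 50% rate ranges from none to 5.6 points as the response among excluded patients goes from 50% down to 0; above 50% it reverses. The contrast can move either way. These sizes rest on assumed response rates, on assumed unequal losses and, in the table, on every excluded patient being a non-responder. They show what is possible and do not forecast the result.

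The endpoint is secondary, and the primary conclusion is unaffected.

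**What to change.** Analyse the HbA1c targets with all visits, by one of two routes:

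- **Impute, then dichotomise.** Multiply impute week-26 HbA1c under missing at random from the patient's own arm and earlier on-treatment values, apply the 7.0% and 6.5% cut-offs, fit the planned logistic regression and combine. The imputation in SAP 6.9.2.3 cannot simply be reused: it draws on the placebo arm to explore data missing not at random.
- **Longitudinal logistic model.** Follow the weight-target model, with visit, treatment-by-visit and continuous baseline HbA1c. State that estimation is likelihood-based and not by GEE; the SAP leaves this open for the weight targets too.

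Either route assumes that the HbA1c history carries enough of the information behind rescue and discontinuation.

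State the denominator for every reported proportion. Add a sensitivity analysis that counts rescued or discontinued patients as non-responders, labelled as answering a different, composite question.

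The cost is SAP wording and minor programming. The reported percentages may be less favourable.
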